Cancer survivors will be asked for consent at the time of registration with YASU or (in the case of those who have already registered) with an email sent to describe study and providing an opportunity to give consent and participate in the registry. Baseline and annual follow-up data will be collected according to the table below. In addition, participation in organizational sponsored programs (e.g., socials, support groups, financial assistance) will be recorded and included in the research registry.

	Instrument	# Items (Approx. time)	Assessment Time Points	
			Baseline	6 mos., then Yearly
Demographics Race Gender DOB Address			✓ ✓ ✓ ✓	
Disease and treatment information Age at Diagnosis Type of cancer Stage Treatment			✓ ✓ ✓ ✓	
Change in disease or treatment	Compared to a year ago, is your health: better, about the same, or worse [If better or worse, then allow free text to explain why]			✓
Depression	PHQ-9	9 (2 min)	✓	✓
Anxiety	GAD-7	7 (1-2 min)	✓	✓
Distress	Distress Thermometer (included in AYA-POST)	1 (30 sec)	✓	✓
Needs Assessment	AYA Psycho-Oncology Screening Tool (AYA-POST)	50 (5 min)	✓	
Financial Toxicity	COST – FACIT (Ver 2)	12 (3 min)	✓	✓
Social support survey instrument	MOS Social Support Survey Instrument	19 (5 min)	✓	✓

Baseline= day of enrollment in the program

Surveys completed ±2 weeks from targeted timeframe

Registry Duration

Registry enrollment will be ongoing. Participants will remain active in the registry until they voluntarily withdraw or expire. Any data that has been provided up until that point will continue to be included in the registry.

Data Management and Quality Plan

Data De-identification

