Participants will be assigned a unique identifier instead of using their names, however other unique identifiers may still be included in the dataset (e.g., zip code and date of birth). The unique identifier will automatically be assigned by Salesforce based on the order of enrollment in the research registry. For instance, the first person to enroll in the research registry would be assigned 0001, the second would be assigned 0002, and so on. A spreadsheet will automatically be created in Salesforce when YASU members enroll in the research registry which will link the unique identifier to the participants. This spreadsheet will be stored in Salesforce separately from the registry dataset. The PI and YASU staff members may be granted access to this information as well as future research collaborators. We plan to keep this linking information available indefinitely. The link between the subject's identity and the assigned registry number may be broken if it becomes necessary to clarify survey responses or if survey responses require reaching out to the individual to provide resources (e.g., reporting on the PHQ-9 plans to harm or kill themselves or others).

Data Confidentiality, Storage, and Retention

Registry documentation and data will be stored electronically within Salesforce. Salesforce contributes to keeping ePHI secure in the Salesforce Covered Services by implementing security safeguards that apply to all customers by default such as:

- Continually monitoring the services for security violations
- Encrypting all data in transit
- Storing user passwords in the SHA-256 one-way hash format
- Enabling audit logging that allows system administrators to track certain change activity in the Salesforce Covered Services
- Providing customer administrators with configurable tools to maintain strict password security policies which govern access
- Providing customer administrators with configurable tools to define user profiles and permission sets governing data visibility
- Providing customer administrators with configurable tools to define a company-wide sharing model, a role hierarchy, and security rules governing data access
- Providing customer administrators with configurable tools for field level history monitoring and retention.

Data Quality

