Source data verification is not necessary for this research registry because the electronic surveys *are* the source data. Prior to data analysis, data will be checked for anomalies or outliers which might suggest invalid data entry by participants.

Data Sharing

Original records including identifiable data will be available to members of the research team and YASU organization for an indefinite period of time. Data may be shared with other researchers/groups with objectives inside or outside the primary aims of this study. In order to be granted access to our dataset, the outside researcher would need to secure IRB approval from an IRB for their proposed study and then would sign a YASU-provided confidentiality agreement. Datasets shared with researchers outside of YASU will not include identifiers. This new data may be made available to the general public via the Internet and an open database. This information will not have participants name or other personally identifiable information included (i.e. it will be de-identified).

Future research collaborators outside of YASU may use the registry to contact participants for other studies and may have access to the linked Salesforce spreadsheet to screen for candidates. Outside researchers who wish to use contacts from the YASU research registry in recruitment for their study will be required to secure IRB approval for their proposed study and to complete the YASU-provided confidentiality agreement prior to any possible participant contact information being shared. Once IRB-approval has been received and the agreement is completed, the PI (and/or YASU executive director) may grant the requestor access to the requested information.

Registry Data Points

All data will be collected via electronic survey as described earlier.

Initial baseline demographics will be collected at the time of registry enrollment and will include self-reported date of birth, race, gender, and address.

Disease and treatment information will be collected via self-report at the time of consent to the research registry. Self-reported information that will be collected include age at diagnosis, type of cancer, stage, and treatment received.

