Patient Health Questionnaire 9 (PHQ-9) (Pfizer, 2010): The PHQ-9 is a 9-item self-reported instrument designed to assess depressive symptoms. For each of the questions, individuals choose one of the following responses regarding how they have been feeling in the past two weeks: Not at all (0), Several days (1), More than half the days (2), or nearly every day (3). The responses can be summed together to yield a total score from 0-27, with higher scores indicating more depressive symptoms. The PHQ-9 will be completed electronically via survey at baseline and annually.

Generalized Anxiety Disorder (GAD-7) (Pfizer, 2010): The GAD-7 is a self-administered 7-item instrument to measure anxiety symptom severity. Like the PHQ-9, individuals think about how they have been feeling in the past two weeks and choose from the following answers: Not at all

(0), Several days (1), More than half the days (2), or nearly every day (3). Total scores range from 0-21, with higher scores indicating greater anxiety symptom severity.

Adolescent and Young Adult Psycho-Oncology Screening Tool (AYA-POST) (Patterson et al., 2022): The AYA-POST provides a psychosocial screening and assessment for people diagnosed with cancer. The tool comprises a distress thermometer and age-specific needs assessment. The distress thermometer quantifies the amount of self-reported distress an individual has experienced over the past week ranging from 0 (no distress) to 10 (high distress). The needs assessment identifies areas of distress or concern in the following categories: practical, family, emotional, social, physical, information, and other (which allows for free response).

Comprehensive Score for financial Toxicity-Functional Assessment of Chronic Illness Therapy (COST-FACIT) (Version 2) (FACITgroup, 2017): The COST-FACIT is a 12-item patient reported measure of financial distress for cancer patients. The measure provides a summary score for financial toxicity. Scores range from 0-44 with higher scores indicating better financial wellbeing.

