Security measures in place to prevent breach of confidentiality from happening (e.g. using Salesforce, an application that upholds HIPAA privacy and security measures; employing features such as limiting access to identifiable data to only users that are associated with the registry).

Participants' responses to the depression inventory scale (PHQ-9) will be monitored. Resources for those that report suicidality will be provided including a suicide hotline and links to mental health resources.

Provisions to Protect the Privacy Interest of Registry Participants

All precautions will be taken to make sure that only authorized individuals will be accessing subject research records. The collection of sensitive information about subjects is limited to the amount necessary to achieve the aims of the research registry, so that no unneeded sensitive information is being collected.

Early Withdrawal of Subjects

Investigator Withdrawal of Subjects

Research registry participants will continue to be surveyed annually. If a participant does not complete surveys within the 4-week "grace period" (± 2 weeks from targeted timeframe) the survivor will not be withdrawn from the registry, but these surveys will be considered as missing data in the data set.

Subject Request for Withdrawal from Registry

Patients wishing to withdraw their data from the research registry will be directed to contact the principal investigator. From the point of withdrawal, no further data will be collected from the patient or their medical records. However, any data collected up to the point of withdrawal will be maintained for integrity of the research registry. Patients will be made aware of their rights in the consent.

Data Collection and Follow-up for Withdrawn Subjects

Patients who withdraw from the registry will have their data maintained in the research database up to the point of withdrawal. This data will be included in subsequent analysis.

Adverse Event Reporting

Adverse Events

N/A; This is an observational registry that does not include a planned intervention or exposure.

Ethical Considerations

N/A

Sharing of Results with Subjects

Individual participant results will not be shared with subjects or others. General results from aggregate data may be shared with participants.

Funding Source

Staunton Farm Foundation (07/01/23-06/30/24)

Elsie H. Hillman Foundation (07/01/23-06/30/25)

Subject Stipends or Payments

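### Aim 2 tests whether YASU programming improves mood and distress, but outside mental-health care is not measured, so the estimate could be biased in either direction

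*Combined protocol and SAP*

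**What the plan says.** Under Statistical Analysis Plan, Aim 1 describes the measures at baseline and uses repeated measures ANOVA for change. Aim 2 is framed as establishing whether YASU programming is effective, through a longitudinal mediation analysis for which natural effect models are given as an example. It names no comparator, confounders or handling of other care.

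On support received, Data Collection Schedule says that "participation in organizational sponsored programs (e.g., socials, support groups, financial assistance) will be recorded and included in the research registry". No other source of support is listed.

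Three listed items come near to mental-health care:

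- Baseline disease information (Registry Data Points): "Self-reported information that will be collected include age at diagnosis, type of cancer, stage, and treatment received".
- A follow-up row on change in disease or treatment (Data Collection Schedule). It asks whether general health is better, the same or worse than a year ago, with the instruction "If better or worse, then allow free text to explain why".
- The AYA-POST: "The needs assessment identifies areas of distress or concern in the following categories". It records concerns, not care received, and the schedule ticks the needs assessment at baseline only.

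The registry also responds to some answers. Mitigation of Risks says that participants' "responses to the depression inventory scale (PHQ-9) will be monitored" and that "Resources for those that report suicidality will be provided including a suicide hotline and links to mental health resources". Data De-identification allows the link to identity to be used "if survey responses require reaching out to the individual to provide resources", with a reported plan of harm to self or others on the PHQ-9 as its example. Under Adverse Events the protocol states: "This is an observational registry that does not include a planned intervention or exposure".

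**The concern.** PHQ-9, GAD-7 and distress are outcomes for an effectiveness question, and people with these symptoms may also seek help elsewhere. Suppose a member attends two support groups and starts counselling in the same half-year. The structured data show only the groups and the later score. A non-attender who starts medication shows only an improved score. The first pattern flatters YASU and the second hides any benefit. Adjusting for baseline PHQ-9 does not deal with care that begins after baseline.

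The gap is hard to repair later. Registry Data Points says that all data come by electronic survey, and Research Design says that they are self-reported and unconfirmed. The withdrawal text mentions medical records in passing, but no extraction from them is planned. Each survey wave fielded without the item leaves start dates to later recall.

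**Working it through.** The plan states no sample size, effect size, SD or care-uptake figure, so there is no figure to reproduce. The check has two parts: what the data set would hold, and how large a bias could be under stated assumptions.

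**1. What the data set would hold**

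| Information needed for Aim 2 | Structured field? | What exists instead |
|---|---|---|
| YASU programme use | Yes | – |
| Counselling or mood/anxiety medication at baseline | No | Treatment listed with disease information |
| The same at follow-up | No | Free text, shown only if general health is better or worse |
| Start date of outside care | No | – |
| Contact by the registry after a PHQ-9 answer | No | The PHQ-9 answers themselves, at each survey |

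A participant who starts therapy but rates general health as unchanged is never shown the free-text box. One who is shown it may write about something else.

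**2. Bias in a user versus non-user contrast**

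Assume that care changes PHQ-9 by the same *d* points in both groups, that the groups are otherwise alike, and that care is not itself a result of attending. Then

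bias = *d* × (care rate in users − care rate in non-users).

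All inputs are assumed:

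- Uptake 30% v 15%, *d* = 3: 3 × 0.15 = 0.45 points in favour of YASU.
- Uptake 30% v 15%, *d* = 5: 5 × 0.15 = 0.75 points in favour of YASU.
- The same rates reversed (15% v 30%): 0.45 to 0.75 points against YASU.
- Equal uptake, for example 30% v 30%: zero.
- A gap of 30 percentage points: 3 × 0.30 = 0.90 to 5 × 0.30 = 1.50 points, either way.

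With smaller effects (*d* from 1 to 4) and rates from 40% v 20% to 20% v 40%, the bias runs from +0.8 through 0 to −0.8 (4 × 0.20 = 0.8). The PHQ-9 total runs from 0 to 27.

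**3. The registry's own outreach**

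Shift in the whole-cohort mean = share flagged × effect of outreach. With 2% to 15% flagged and an effect of 1 to 5 points (assumed), this is 0.02 × 1 = 0.02 to 0.15 × 5 = 0.75 points. A middle case, 5% flagged and 3 points, gives 0.05 × 3 = 0.15. The top of the range needs both a high share flagged and a large effect from a hotline and links. Monitoring also covers all participants, so in a user versus non-user contrast it largely cancels unless the flagged share differs between the groups.

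**The case against.** The strongest reply is that the outreach does not produce the bias. It is tied to suicidality or harm, not to a high total score. It consists of a hotline and links, and it applies whether or not a member uses YASU programmes. No trigger on the GAD-7 is stated. Any gap in outside care between users and non-users would have to come from ordinary help-seeking, on which the documents are silent. All of this stands. Unmeasured outside care is therefore the main point and the outreach log is secondary. The anxiety part rests on unmeasured care in general.

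A reader might infer that falls in depression and anxiety scores will be credited to YASU. The documents do not support that. Aim 1's ANOVA describes change and attributes nothing to programming. Aim 2 specifies no contrast that fixes the sign, and non-users may be the ones who already have a therapist.

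A reader might also infer that care after baseline is wholly invisible. It is not: the follow-up free text could catch some of it, and the PHQ-9 answers show who reported suicidality and when. Neither gives a usable care variable with dates, and the answers do not show whether contact followed.

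A further objection concerns the remedy. A support group may prompt someone to seek counselling, so adjusting for later care can remove part of the programme's effect. Dropping people who began care selects on an event after exposure. Both criticisms are right and they shape the fix.

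Finally, Aim 2 lacks a full confounder set, of which this is one element. That is true, but most of such a set can be written into the SAP later. A variable that was never collected cannot.

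**Conclusion.** The concern holds as a measurement gap. Aim 2 seeks an effectiveness conclusion for PHQ-9, GAD-7 and distress while a plausible major confounder has no structured field at any time point. The resulting error could favour YASU, be nil, or go against it. Because the sign is unknown, the estimate cannot be defended as conservative.

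The illustrative size is 0.45 to 0.75 PHQ-9 points either way, or 0.90 to 1.50 if uptake differs by 30 percentage points. These figures rest entirely on assumed uptake and effect, and on care not being a consequence of attendance. If attendance leads to care, that part of the difference belongs to the programme's total effect and is not bias. The data are needed in either case to tell the two apart.

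The statement of no planned intervention is weak evidence of a contradiction, since a safety response need not be a study intervention. It would still help to reconcile it with the monitoring and outreach text.

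**What to change.** **Data.** Add one item to the baseline survey and every follow-up survey: counselling or medication for mood or anxiety received (yes/no), month started, and current (yes/no). Use a six-month look-back at baseline and the 6-month survey, and one year at the yearly surveys. Enter the date of each PHQ-9-triggered contact in the registry data set.

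**SAP, Aim 2.** Adjust for care already in place before programme exposure. State in advance whether care that starts after exposure is treated as a time-varying confounder, using a method suited to that such as marginal structural weighting, or as part of the programme's pathway. Do not simply condition on it. Any analysis that excludes people who began care should appear only as a labelled sensitivity analysis.

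**Cost.** About 30 seconds per survey, one log field and a short SAP paragraph. The downside is one more sensitive item, which should be named in the information sheet. It is consistent with the protocol's own limit on sensitive data, because Aim 2 needs it.

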This registry will prospectively collect data from young adult cancer survivors using electronic surveys to describe patient-reported needs and outcomes at baseline as well as changes over time. Please note that all information collected for this registry is self-reported and not confirmed.

Registry Site(s)/Location(s) and Number of Subjects

YASU website registration page: yasurvivors.org

Total number of all sites: 1

Estimated number of subjects at all sites combined: undetermined. ongoing recruitment will occur as members register with the organization.

Subject Selection

Vulnerable Populations (if applicable)

N/A

Participant Selection

Inclusion Criteria

1. Diagnosed with cancer between the ages of 18 and 39.
2. Able to speak and read English.

This registry is designed to explore the specific concerns, needs, and outcomes of those diagnosed with cancer as YAs (ages 18-39). Potential participants will be required to comprehend English as some of the surveys we will administer have not been validated in other languages. Additionally, YASUs programming is conducted in English. Without the ability to comprehend English, individuals would not be able to participate in YASU programming and we would not be able to test for possible mediation, as listed in Aim 2.

Exclusion Criteria

1. Inability to provide consent (such as neurological illness or mental incapacity)
2. Has not registered as a member of YASU

Waiver of Written Documentation of Consent or Waiver of Consent

We are applying for a Waiver of Written documentation of Consent (consent will be obtained but signatures will not be required) as this study is minimal risk and will be conducted completely electronically.

Registry Procedures

Specific Training

After IRB approval and prior to study initiation, the PI will meet with members of the YASU organization to explain the registry and procedures for consent and data collection and their roles and duties including answering any questions or concerns that may arise. Besides an email sent to current YASU members inquiring about their interest in research registry participation, the consent for new members and ongoing surveys for those who consent to participate will be automatically triggered and sent (using Salesforce) so we do not anticipate needing significant involvement from YASU organizational staff members for ongoing study management.

Recruitment of participants

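### The plan specifies no structured item on whether anticancer treatment is ongoing or when it ended, so a plausible confounder of the Aim 2 programme effect would be captured only in part

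*Combined protocol and SAP*

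**What the plan says.** Registry Data Points gives the timing of the disease items ("Disease and treatment information will be collected via self-report at the time of consent to the research registry") and then their content: "Self-reported information that will be collected include age at diagnosis, type of cancer, stage, and treatment received". The Data Collection Schedule table has the same four fields in one row ("Disease and treatment information Age at Diagnosis Type of cancer Stage Treatment"), ticked at baseline only. Neither place mentions current treatment status or a start or end date.

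At 6 months and then yearly, the table has one row on change in disease or treatment. Its question is "Compared to a year ago, is your health: better, about the same, or worse", with free text allowed if the answer is better or worse. It is not asked at baseline.

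No other source is described that could fill the gap. Registry Data Points says "All data will be collected via electronic survey as described earlier", and Research Design adds "Please note that all information collected for this registry is self-reported and not confirmed".

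The only disease criterion under Inclusion Criteria is "Diagnosed with cancer between the ages of 18 and 39". It sets no limit on treatment phase or time since diagnosis. People who are not YASU members are excluded. Programme participation is recorded, not assigned.

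The Statistical Analysis Plan names repeated measures ANOVA for Aim 1 and a longitudinal mediation analysis, such as natural effect models, for Aim 2. It lists no covariates or confounders for either.

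**The concern.** A member in the middle of treatment and a member who finished some time ago enter the registry on the same terms. Both can truthfully give the same answer to an item on treatment received.

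Treatment phase plausibly acts on depression, anxiety, distress and financial toxicity scores, and also on whether a member is able or inclined to attend programmes. A variable that bears on both participation and outcome is a confounder of the Aim 2 question. With no assignment and no non-member comparison, adjustment for measured confounders is the main protection Aim 2 has, and natural effect models depend on those confounders being measured. A status that was never recorded at the time can be recovered later only by recall.

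For Aim 1, the average change over time would pool members whose treatment ends during follow-up with members long past it, and there would be no field by which to separate them.

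**Working it through.** The plan states no figure on this point, so the check is whether the planned fields can stand in for treatment phase. An illustration of size on assumed inputs follows.

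**1. Baseline fields.** The text and the table agree on four items: age at diagnosis, type, stage and treatment received. None of them is treatment status or an end date.

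**2. Time since diagnosis as a substitute.** Date of birth is also collected at baseline. Date of birth plus age at diagnosis, if age is recorded in whole years, places the diagnosis within a 12-month window. Subtracting this from the enrolment date gives time since diagnosis to within about a year. That usually separates a long-term survivor from a recent diagnosis. It does not separate on-treatment from off-treatment members among recent diagnoses or those on prolonged treatment, because time since diagnosis is not time since treatment.

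**3. The follow-up row as a substitute.** Its reference point is 12 months before each survey. The stipend section names follow-ups at 6, 12 and 24 months.
- 6-month survey: 6 − 12 = −6, so the comparison is with a time 6 months before baseline.
- 12-month survey: 12 − 12 = 0, so the comparison is with baseline.
- 24-month survey: 24 − 12 = 12, so the comparison is with the previous survey.

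(Each survey may move by the ±2-week window.) At 6 months the question therefore mixes change before and after enrolment. At every survey, a member who finished treatment but feels about the same gets no free-text prompt and leaves no record. A member who does get the prompt may or may not mention treatment.

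**4. Who can enrol and who attends.** Any treatment phase is eligible, participation is self-selected, and no adjustment set is named. The conditions for confounding by treatment phase are therefore plausible, and the planned fields measure phase only in part.

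**5. Illustrative size for Aim 2 (every input assumed; none is in the documents).** Let g be the PHQ-9 improvement on finishing treatment, and d the difference between higher and lower programme participants in the share finishing during follow-up. The bias in an unadjusted contrast is g × d.
- Low: 1 × 0.10 = 0.1 points.
- High: 3 × 0.30 = 0.9 points.

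The PHQ-9 runs from 0 to 27. If lower participants are the ones more likely to finish, d is negative and the range becomes −0.1 to −0.9.

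**6. Illustrative size for a before-after average (same status).** With p the share of all members finishing during follow-up, the shift is g × p: from 1 × 0.2 = 0.2 to 3 × 0.5 = 1.5 points. This is part of the Aim 1 average change. It is not the bias in a programme contrast.

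**The case against.** The strongest reply is that the plan does not ignore the topic. It has a follow-up row labelled for change in disease or treatment, and a member who improves because treatment ended would be shown the free-text box. Time since diagnosis can be approximated. The survey form itself is not in the documents: the treatment field is only a label and may carry sub-questions, and the needs-assessment items are not reproduced either.

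Most of this stands, and it limits what can be claimed. A reader might infer that recovery after treatment and a programme effect cannot be told apart at all. The documents do not support that, since time since diagnosis and free text give partial information. A reader might also infer that the survey fails to ask about current treatment. The documents support only that the protocol does not specify such an item. What remains is that the row labelled for treatment change does not ask about treatment, is absent at baseline, and prompts an explanation only when health has changed.

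A second reply is that the missing item is not what blocks Aim 2: self-selection, the absence of non-members and the unnamed adjustment set would remain if it were added. That is correct. Measuring treatment phase is necessary for a credible adjustment but not sufficient.

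A third reply is that an average over the whole membership is a legitimate description for Aim 1. This also stands. The pooled average is coarse, not invalid, and reporting by phase is a refinement.

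**Conclusion.** The point holds as a gap in what is specified for collection. No structured item gives current treatment status or end date, and the existing follow-up row and time since diagnosis make up for this only in part. Treatment phase is therefore a plausible confounder of the Aim 2 programme effect that could not be adequately adjusted for.

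The size and direction of the bias are unknown from the documents. The 0.1 to 0.9 PHQ-9 points above rest wholly on assumed values and show only that the bias could be anything from negligible to noticeable. It would be tempting to conclude that the gap inflates the apparent benefit of YASU programmes, with members recovering and attending more together. Nothing in the documents shows that attendance rises as treatment ends. If on-treatment members attend more, the sign could reverse.

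The conclusion assumes that treatment phase relates to both symptoms and attendance, and that the survey form has no relevant sub-question that the protocol leaves out. If such a question exists, listing it in the protocol would meet the data-collection part of the point.

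**What to change.** - **Baseline:** extend the treatment item with a structured current-status question: active; maintenance or hormonal; or finished, with month and year of last treatment.
- **Follow-up:** revise the existing row on change in disease or treatment to ask the same question, plus any recurrence or new treatment since the last survey. Using the last survey as the reference also removes the mismatch at 6 months.
- **Aim 1:** report baseline values and change by treatment phase.
- **Aim 2:** name both baseline phase and time-varying treatment status in the adjustment set. Baseline phase alone would miss treatment that ends during follow-up.

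The cost is a few seconds per survey, some recall error in self-reported dates, and a sentence or two in the Statistical Analysis Plan. For scale, the table's instrument times sum at baseline to 2 + (1 to 2) + 5 + 3 + 5 = 16 to 17 minutes, counting the distress item within the needs tool.

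The change is best made early. Registry Duration says "Registry enrollment will be ongoing. Participants will remain active in the registry until they voluntarily withdraw or expire", so each further enrolment without the item adds a member whose baseline phase would have to be recalled later.

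The change reduces confounding but does not remove it. Other self-selection into programmes and the lack of a non-member comparison group remain, and any Aim 2 report should say so.
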